#### 2.7. Impact on Safety

There are no new impacts on safety with a reduction to half-hour daily stimulation. One potential risk is that half-hour daily stimulation will not be as effective in treating UUI symptoms as 2 hours daily stimulation, and, in this case, subjects may choose to revert to 2 hours daily stimulation.

#### 3. ETHICS AND REPORTING

All the ethical elements and reporting requirements as stated in the SANS-UUI protocol will be followed.

#### 3.1. Written Informed Consent

The Informed Consent Addendum for this sub-study must be approved in writing by an IRB or EC, as applicable. Written Informed Consent must be obtained prior to any sub-study-related procedure. To reduce the burden on subjects, the Informed Consent process can be completed remotely (i.e., by mail and telephone). Each site will follow their process for obtaining and documenting for Informed Consent.

16 MAR 2024

Statistical Analysis Plan			nge 2 of 25
Sponsor	Study		Version
Neuspera	Clinical Study of Neuspera's Implantable Sacral Nerve Stimulation (SNS) System in Patients with Symptoms of Urinary Urgency Incontinence (UUI)		17.0

Version History

Version	Version Date	Author/Title	Summary of Key Changes
1.0	21May2019	[name]/Statistician NAMSA	Initial Release
2.0	22Jul2019	[name]/Statistician NAMSA	Refined analysis populations and added performance goal discussion
3.0	30Oct2019	[name]/Statistician NAMSA	Updates made to be in alignment with protocol version 5.0 list of secondary endpoints.
4.0	05Dec2019	[name]/Statistician NAMSA	Updated NSM-004 protocol reference in document to most current version of protocol (V6 dated 05 December 2019)
5.0	25Feb2020	[name]/Statistician NAMSA	Updated NSM-004 protocol reference in document to most current version of protocol (V7 dated 28 January 2020)
6.0	8 May 2020	[name]/Statistician NAMSA	Updated NSM-004 protocol reference in the document to most current version of protocol (V9 dated 20 May 2020)
7.0	30 July 2020	[name]/Statistician NAMSA	Updated NSM-004 protocol reference in the document to most current version of protocol (V10 dated 17 July 2020)
8.0	06 Oct 2020	[name]/Statistician Covance	Updated NSM-004 protocol reference in the document to the most current version of protocol (V11.0 dated 06 October 2020). Changed number of subjects in Phase I to may be up to a total of 55, as indicated in protocol V11.0. Added section defining enrollment.

Statistical Analysis Plan Pa			age 3 of 25
Sponsor	Study		Version
Neuspera	Clinical Study of Neuspera's Implantable Sacral Nerve Stimulation (SNS) System in Patients with Symptoms of Urinary Urgency Incontinence (UUI)		17.0

Version	Version Date	Author/Title	Summary of Key Changes
9.0	15 January 2021	[name]/Statistician Covance	Added analysis plan for hierarchical testing of secondary endpoints intended for labeling claims. Added null and alternative hypotheses for secondary endpoints intended for labeling claims. Updated definitions of analysis populations. Updated sample size. Updated design to remove references to trial period. Follow-up period begins after implant.
10.0	16 March 2021	[name]/Statistician Covance	Updated definitions of analysis populations. Elaborated on treatment of missing data for the primary and secondary efficacy endpoints intended for labeling claims.
11.0	16 July 2021	[name]/Statistician LabCorp	Added references for clinical justification of efficacy endpoint. Added Monitoring of Phase II Safety Data for DSMB review.

Statistical Analysis Plan		Pa	ige 4 of 25
Sponsor	Study		Version
Neuspera	Clinical Study of Neuspera's Implantable Sacral Nerve Stimulation (SNS) System in Patients with Symptoms of Urinary Urgency Incontinence (UUI)		17.0

Version	Version Date	Author/Title	Summary of Key Changes
12.0	17 November 2021	[name]/Statistician LabCorp	Clarified that physician and subject satisfaction secondary endpoints are evaluated at 6 months. Updated surgical revision rates and added references. Added Phase II stopping rules and rational for stopping rules. Added formal mathematical statements for probabilities that Phase II event rates exceed comparator event rates.
13.0	08 March 2022	[name]/Statistician Labcorp	Updated Phase II stopping rules for continual monitoring of device fracture, dislodgement/migration, and surgical revisions. Updated actions taken if a stopping rule is met. Updated secondary endpoints to match exactly the protocol synopsis and Statistical Consideration section of the protocol.
14.0	26 April 2022	[name]/Statistician NAMSA	Updated Phase II study design to group sequential, allowing for an analysis of the primary efficacy endpoint when 50% of subjects have completed 6-months of follow-up. Added language regarding a sensitivity analysis of the primary efficacy endpoint that will be performed accounting for subjects that used OAB medication during study follow-up

Statistical Analysis Plan			ige 5 of 25
Sponsor	Study		Version
Neuspera	Clinical Study of Neuspera's Implantable Sacral Nerve Stimulation (SNS) System in Patients with Symptoms of Urinary Urgency Incontinence (UUI)		17.0

Version	Version Date	Author/Title	Summary of Key Changes
Version 15.0	Version Date 7 April 2023	Author/Title [name] Statistician Summit Analytical	 Updated SAP based on changes made to protocol V18 (05APR2023). Added new Intent-to-Treat (ITT) analysis set and updated original ITT analysis set to Modified ITT analysis set. Added new secondary efficacy endpoint (change in urgent voids per day). Clarified that secondary efficacy endpoints may be used for labeling claims instead of intending to be used for labeling claims.
			claims instead of intending to be used
			for labeling claims. • Updated interim analysis section.

Statistical Analysis Plan Pa			ige 6 of 25
Sponsor	Study		Version
Neuspera	Clinical Study of Neuspera's Implantable Sacral Nerve Stimulation (SNS) System in Patients with Symptoms of Urinary Urgency Incontinence (UUI)		17.0

Version	Version Date	Author/Title	Summary of Key Changes
16.0	12 June 2023	[name] Statistician Summit Analytical	 Updated SAP based on changes made to protocol V19 (12June2023) Noted that no more than 5 sites will be included from Europe and Canada, and more than 50% of subjects enrolled will be from the United States. Lowered the number of attempted implants from 145 to 120. Lower the power for a one-sided 0.025 exact binomial test from 90 to 85%. Increased number of clinical sites from 25 to 35. Updated the "worst case" scenario results that would still meet the statistical threshold for this performance goal, changed to 72 out of 120 (60%). Updated the assumed population responder rate from 64% to 63.5%. Included site and region (US vs. OUS) as subgroups. Added a ICIQ-OABqol responder rate secondary endpoint to be potentially used for labeling claims. Updated information on PMA submission to match protocol. Updated details on interim analysis. Added Coyne, et al reference and renumbered Bibliography

Statistical Analysis Plan P			nge 7 of 25
Sponsor	Study		Version
Neuspera	Clinical Study of Neuspera's Implantable Sacral Nerve Stimulation (SNS) System in Patients with Symptoms of Urinary Urgency Incontinence (UUI)		17.0

Version	Version Date	Author/Title	Summary of Key Changes
17.0	16 Mar 2024	[name]/Statistician Fortrea	 Update language regarding failures for primary efficacy endpoint to explicitly count explants/withdrawals and subjects taking OAB medications as failures Note that subgroup analysis is exploratory and not to be used for labeling purposes Refine secondary endpoints per FDA feedback; clarify analysis of ICIQ-OABqol is to be calculated according to published criteria

Statistical Analysis Plan Pa			age 8 of 25
Sponsor	Sponsor Study		
Neuspera	Clinical Study of Neuspera's Implantable Sacral Nerve Stimulation (SNS) System in Patients with Symptoms of Urinary Urgency Incontinence (UUI)		17.0

Document Approval

Approval	
Approved By	[name]
Signature	
Date	
Role	Biostatistician, Fortrea

Approval	
Approved By	[name]
Signature	
Date	
Role	VP, Clinical, Quality, and Regulatory Affairs

Statistical Analysis Plan Pa			ige 9 of 25
Sponsor	Study		Version

The overall objective of the study is to assess the safety and efficacy of the Neuspera Implantable SNS System for treatment of Urinary Urgency (UUI) based on Phase II results, following the determination of daily stimulation settings as informed by Phase I. Accordingly, hypotheses and formal endpoints are primarily based on results of Phase II. Unless otherwise specified, all analyses described in this section refer to the analysis of data gathered only under Phase II. Analyses for Phase I will consist of descriptive statistics since stand-alone definitive conclusions regarding safety or efficacy from this phase cannot be concluded due to the small sample size. The purpose of Phase I is simply to inform stimulation duration for Phase II.

3 Study Design

The study is a prospective, multi-center, single-arm, seamless phased pivotal study. The study population consists of subjects diagnosed with UUI who have failed or could not tolerate more conservative treatment.

The study will be conducted in two phases: Phase I may enroll up to 55 subjects in order to assess the utilization of the system during the SNS trial period and to help inform the length of hours of daily stimulation to be used in the second phase; Phase II may enroll up to 255 subjects (a separate group from Phase I subjects) to assess the safety and efficacy of the Neuspera SNS system at 6 months for the primary efficacy endpoint, and again at 12 months for the secondary safety and efficacy endpoints. The study is an operationally seamless design (in contrast to an inferentially seamless design). Accordingly, the formal statistical conclusions are to be based on solely Phase II. As there is no overlap of subjects, and the design of Phase II is fixed (i.e. there is no sample size re-estimation or other adaptive design elements), there are no bias or type I error concerns.

Statistical Analysis Plan Pa			ge 11 of 25
Sponsor	Study		Version
Neuspera	Clinical Study of Neuspera's Implantable Sacral Nerve Stimulation (SNS) System in Patients with Symptoms of Urinary Urgency Incontinence (UUI)		17.0

Phase I analysis may occur at several points during the trial as the sponsor wishes to assess compliance and the performance of the system as this will be the first chronic use of the system (See section 5.10 Interim Analysis). An interim analysis of Phase I data will occur at the discretion of the sponsor. The data from Phase I will not be the basis for formal conclusions; the intent is to gain initial data to inform the stimulation duration for Phase II.

A primary efficacy endpoint analysis of Phase II will occur when all subjects have completed 6 months post-implant (or are exited from the study). An interim analysis will be performed when the 60th Phase II subject has completed the 3-month post implant visit.

Sections 5.7 and 5.10 provide additional details on the timing of the analyses and planned interim analyses, respectively. All subjects are anticipated to be enrolled and implanted prior to the Phase II interim analysis. The Phase II interim analysis will be conducted by an independent statistician.

Regardless of the outcome of the interim analysis, the study will enroll to its planned sample size and all subjects will complete their scheduled follow-up (unless they are exited from the study). If the interim analysis is not successful, but the primary endpoint is achieved at the end of six months of follow-up, the sponsor intends to file the PMA submission.

It is expected that no more than 5 sites to be included from Europe and Canada. More than 50% of the subjects enrolled will be from the United States.

4 Sample Size Determination

Sample size for Phase I is not based on power requirements for a statistical hypothesis test, but for a desire to obtain a reasonable initial sample size to inform Phase II in a timely fashion. It is anticipated that approximately 33% of implanted subjects will not respond to SNS therapy during the trialing period or drop out for other reasons. It is also expected that some subjects may not demonstrate appropriate motor response during intra-operative testing. Therefore, to account for subjects in whom implant is attempted but the system is not implanted, up to 55 subjects may need to be enrolled to implant up to 40 subjects for 20-27 subjects to proceed post-trialing period in Phase I.

Sample size for Phase II is based on power requirements for the primary efficacy endpoint. A total of 120 attempted implants will provide 85% power for a one-sided 0.025 exact binomial test against the null hypothesis assuming that 1) the implant success rate is 95%, 2) subjects in whom implants are attempted but are not successful are counted as failures, and 3) the overall responder rate, including failed implant attempts, is 63.5%. Calculations are based on a one-sample, one-sided exact test of binomial proportions with a normal approximation and were performed with PASS 2019. To account for

Statistical Analysis Plan Pa			ge 12 of 25
Sponsor	Study		Version
Neuspera	Neuspera Clinical Study of Neuspera's Implantable Sacral Nerve Stimulation (SNS) System in Patients with Symptoms of Urinary Urgency Incontinence (UUI)		17.0

potential attrition prior to implant of up to approximately 43% including screen failures, up to 255 subjects will be enrolled/consented in Phase II. Revisions will not count towards attempted implants. Phase I of the study will be conducted at up to 14 clinical study sites in the US and Europe. Phase II of the study will be conducted in up to 35 clinical sites in the US and Europe. Sample size at any one investigational site will be restricted to no more than 15 subjects enrolled for Phase I and 25 subjects implanted for Phase II. Consideration will be given to lifting the 25 subject implanted cap in Phase II if the investigator makes a request of the sponsor.

5 Statistical Analyses

5.1 General Considerations

Except where otherwise specified, the following general principles apply to the planned statistical analyses. All statistical analysis will be conducted using SAS version 9.4 or later (SAS Institute Inc., Cary, NC) or other widely accepted statistical or graphical software as required.

Unless otherwise noted, analyses will be performed separately for Phase I and II, with the focus of analyses on Phase II. Statistical tests are only planned based on Phase II. Any p-values based on Phase I will be considered exploratory.

5.1.1 Descriptive Statistics

Continuous data will be summarized with mean, standard deviation, median, minimum, maximum, and number of evaluable observations. Categorical variables will be summarized with frequency counts and percentages. Confidence intervals may be presented, where appropriate, using the t-distribution for continuous data and Clopper-Pearson Exact method for categorical variables.

5.1.2 Study Day O/Baseline Assessments

Efficacy assessments that are measured over time will use pre-implant data as baseline.

For safety assessments, study day 0 is based on the date of implant (or date of attempted implant for those subjects attempted but not implanted, or date of replacement for subjects undergoing a replacement prior to the assessment of primary endpoint). Time of the event is based on the onset date for the event and calculated from date of implant (or date of attempted implant, or date of replacement, as appropriate). Specific time points for evaluation of safety events (e.g. 6 months) will be defined based on the corresponding visit date for subjects with a visit, or the close of the corresponding visit window for subjects without an event.

Statistical Analysis Plan Pa			ge 13 of 25
Sponsor	Sponsor Study		
Neuspera	Clinical Study of Neuspera's Implantable Sacral Nerve Stimulation (SNS) System in Patients with Symptoms of Urinary Urgency Incontinence (UUI)		17.0

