## 6.1.3.2 Primary Safety Endpoint

The primary safety endpoint is defined as the incidence of device-related SAEs through the 6-month post-implant visit. The analysis of the endpoint is the proportion of subjects experiencing device-related SAEs through the 6-month post-implant visit.

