# 7.5.8.9 Device Replacements

During the course of the study, subjects may require a replacement of the neurostimulator. If a subject receives a neurostimulator replacement prior to Month 3 clinic visit in Phase I, the subject will repeat trialing and follow-up, as the newly replaced device may not be in the identical location as the previous device (i.e., new location on ipsilateral side, contralateral side or different foramen). If a subject receives a device replacement prior to Month 6 clinic visit in Phase II, the subject will repeat all post-implant

Protocol no: NSM-004; Version 21.0 Page 88 of 141 04 Apr 2025
Confidential Neuspera

procedures including the Day 28 and Day 42 (if needed) response rate assessment and follow-up visits. Both in Phase I and Phase II, the date of replacement will be considered the new device implant date for analysis and follow-up purposes. Subjects with device replacement will begin with procedures listed in Section 7.5.6.6 (Sacral Nerve Stimulation Pre-Implant Assessments), with the exception of the inclusion/exclusion checklist, and continue in the study as outlined following an implant for Phase I or Phase II, as appropriate. If a device replacement is required after the time periods indicated above (Month 3, Phase I; Month 6, Phase II), subjects will be managed as determined best by the investigator to obtain optimal programming settings, that is, no trialing (Phase I) and no response rate assessment (Phase II). Subjects will continue on their original follow-up schedule without repeating any of the assessments or follow-up visits already completed.

The following data will be collected for device replacements:

- Reason for device replacement
- Device Parameter/Download (prior to device explant)
- Replacement/explant procedure data
- Fluoroscopy images for replacement
- Vital Signs
- Changes to medication (including OAB medications) and OAB therapies
- Adverse event assessment (any signs or symptoms associated with the reason for replacement, will be reported as an adverse event)

The explanted neurostimulator should be placed in a biohazard kit and shipped to the Sponsor for investigation. The neurostimulator must be handled carefully and as little as possible to prevent damage and preserve its integrity. The Sponsor must be contacted for shipping and packaging materials and to arrange for transport.

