5.6 Analysis of Study Endpoints

5.6.1 Primary Safety Endpoint

The primary safety endpoint is defined as the incidence of device-related SAEs through the 6-month post-implant follow-up visit. The analysis of the endpoint is the proportion of subjects experiencing a device-related SAE through the 6-month post-implant follow-up.

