5.6.1.1 Primary Safety Analysis

There is no planned statistical hypothesis test for the primary safety endpoint. The proportion of subjects experiencing an event, as well as the numerator and denominator, and the associated two-sided exact 95% binomial confidence interval will be provided. Values will be expressed as percentages.

The primary analysis population for the primary safety endpoint is the mITT Analysis set as defined in Section 5.2. Subjects who exit the study prior to reaching the 6-month post-implant follow-up visit without experiencing a device-related SAE will be assumed free of such an event. Any adverse events reported for enrolled subjects who are excluded from mITT Analysis set will be reported separately for the duration of participation in the study.

Statistical Analysis Plan Pa			ge 15 of 25
Sponsor	Study		Version
Neuspera	Clinical Study of Neuspera's Implantable Sacral Nerve Stimulation (SNS) System in Patients with Symptoms of Urinary Urgency Incontinence (UUI)		17.0

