5.6.3 Secondary Endpoints

The secondary endpoints completed at 6 and 12 months if not indicated differently are below:

s	tatistical Analysis Plan	Pa	ge 17 of 25
Sponsor	Study		Version
Neuspera	Neuspera Clinical Study of Neuspera's Implantable Sacral Nerve Stimulation (SNS) System in Patients with Symptoms of Urinary Urgency Incontinence (UUI)		17.0

- Change from baseline in quality of life as measured and assessed by the total ICIQ-OABqol score.
- Change from baseline in mean number of UUI episodes.
- The percentage of subjects who experience an improvement in UUI symptoms (therapy responders) of at least 50% or more at 12 months visit post implant.
- The percentage of subjects who experience an improvement in ICIQ-OABqol of at least 10 points.
- Change in urgent voids per day calculated across all diary episodes with at least mild urgency.
- Change in average number of daily voids from baseline in subjects with at least 8 voids at baseline.
- Change in quality of life measured from baseline as measured and assessed by the ICIQ-OABqol subscale scores.
- Comprehensive summary of all adverse events (AEs) for the duration of study participation.
- Device parameters including but not limited to voltage, pulse width, frequency, and stimulating electrode.
- Physician and subject satisfaction as assessed with the User Experience Questionnaire at 6month visit post implant.
- Change in Male/Female Lower Urinary Tract Symptoms questionnaire.
- The percentage of subjects with device-related serious adverse events reported through 12-month visit post-implant.
- Change in total urinary output as measured by 72-hour bladder diary.
- Change in fecal incontinence as measured by the Wexner Scale compared to baseline.
 Calculated in subjects with fecal incontinence.
- Patient Global Impression of Improvement (PGI-I) measured after implant during follow-up.

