5.7 Analysis of Replacements, Explants

During the course of the study, it may be necessary for the investigational device to be replaced or permanently explanted from the subject. Revision rates in the literature range from 4% in the InSite studyⁱⁱ to 33% in the Herbison^{vi} study. Depending on the timing of replacements, it may be necessary for the subject's response rate to be reassessed in the first 28 to 42-days post-implant.

During Phase I of the study, if a subject receives a neurostimulator replacement prior to Month 3 clinic visit, the subject will restart their follow-up schedule, and repeat the trialing period and any of the follow-up visits completed prior to replacement. If a subject receives a device replacement prior to the assessment of the primary efficacy endpoint in Phase II (Month 6 clinic visit), the subject will restart their entire follow-up schedule post-implant, including the responder rate assessments at Day 28 and Day 42, if not a responder at Day 28. The date of replacement will be considered the new Device Implant date for analysis and follow-up purposes. If a device replacement is required after the follow-up periods indicated above, subjects will continue on their original follow-up schedule and do not repeat any of the assessments or follow-up visits already completed.

If assessment of the response rate is repeated in the first 28 to 42-days post-implant, data collected after the most recent implant will be used in the analysis. Similarly, if the subject is required to repeat any portion of the post-implant follow-up visits after a replacement (replacement occurred before Month 6 clinic visit), the data from the replacement visit(s) will be used in analysis. The date of replacement will be considered the Device Implant date for analysis and follow-up purposes. A subject is only allowed to repeat any portion of the post-implant period once.

If the device is permanently explanted prior to the assessment of the primary efficacy endpoint for any reason, the subject will be considered a failure for the primary efficacy analysis.

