5.9 Safety Analyses

Investigators are required to report all AEs during the course of the study. Investigators are responsible for providing a description of all AEs, including the date of the event, treatment and the clinical outcomes for the subject. Investigators will evaluate each event for seriousness, severity and relatedness to the procedure, device or stimulation therapy. All adverse events, including unanticipated adverse device effects (UADE), and serious adverse events (SAE) will be reported for all enrolled subjects.

For Phase I, all adverse events reported over the course of the study will be summarized for all enrolled subjects. Any adverse events reported for consented subjects who were not enrolled will be reported separately.

For Phase II, all adverse events reported over the course of the study will be summarized for the mITT analysis set. Any adverse events reported for enrolled (i.e., consented) subjects who are excluded from mITT analysis set will be reported separately.

Adverse events will be tabulated with the number of events and subjects with event for each event type and overall. Rates will be reported as the number of subjects who experience at least one event during the analysis interval out of the total number of subjects with follow-up to the beginning of the analysis interval. Serious adverse events will also be tabulated. The rate of all AEs and SAEs reported in the study will be reported.

All AEs and SAEs will also be summarized by relatedness. Adverse events leading to death or study discontinuation will be provided in a listing format.

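### Safety day 0 restarts at device replacement, so a device-related SAE on the first device can fall out of the 6- and 12-month safety proportions

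*SAP*

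**What the plan says.** SAP 5.1.2 has a day-0 rule specific to safety. Day 0 is the implant date, the date of the attempt if no device was implanted, or the "date of replacement for subjects undergoing a replacement prior to the assessment of primary endpoint". Event time is the onset date counted from whichever of these applies, and the 6-month point is the date of the corresponding visit.

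SAP 5.7 restarts the whole follow-up schedule when a Phase II device is replaced before the Month 6 visit, and adds: "The date of replacement will be considered the new Device Implant date for analysis and follow-up purposes". Protocol 6.3 says the same. Protocol 7.5.8.9 states that "the date of replacement will be considered the new device implant date for analysis and follow-up purposes". None of these places makes an exception for safety.

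SAP 5.6.1 defines the primary safety endpoint as "the incidence of device-related SAEs through the 6-month post-implant follow-up visit". Protocol 6.1.3.2 agrees. SAP 5.6.1.1 reports it in the mITT set as a proportion with a two-sided exact 95% interval and no test. It adds that subjects who leave before the 6-month visit "without experiencing a device-related SAE will be assumed free of such an event". SAP 5.6.3 lists the 12-month counterpart: "The percentage of subjects with device-related serious adverse events reported through 12-month visit post-implant".

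**The concern.** Once the implant date means the replacement date, an SAE on the first device lies before day 0. SAP 5.9 reports AE rates by whether a subject had an event within the analysis interval. A programmer who starts that interval at day 0 and applies the same logic to the endpoint would drop the event and would be following the text. A programmer who reads *through* as cumulative would keep it. No sentence in either document settles the matter.

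The events at risk are informative. Protocol 7.5.8.9 requires signs and symptoms behind a replacement to be reported as adverse events. Where such an event is serious and device-related, the reset can remove from the primary safety numerator the very event that caused the replacement. Because the endpoint has no test, the proportion and its interval are its whole output, and the numerator has to be unambiguous.

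**Working it through.** **The rule on one case (illustrative dates).** First implant on day 0, device-related SAE on day 60, replacement on day 70. Under SAP 5.1.2 the event time is 60 − 70 = −10 days. The 6-month point becomes the Month 6 visit counted from the replacement. An interval from day 0 to that visit excludes the event; a cumulative count up to that visit includes it.

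**Inputs**
- N = 120 attempted implants (SAP section 4); 130 attempts are reported in Protocol 3.1.2.2.2.
- Four subjects with surgical revisions among the 130, and no SADEs to date (Protocol 3.1.2.2.2). How many of the four were replacements before Month 6 is not stated.
- Exact (Clopper-Pearson) 95% limits (SAP 5.6.1.1).
- Visit windows from Protocol Table 8: Month 6 at 180 ± 14 days, Month 9 at 270 ± 14, Month 12 at 360 ± 14, Month 18 at 540 ± 21.

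**Check of the method.** The plan gives no figure for this endpoint, so the limits were checked on its stopping-rule comparators. 6/51 gives 0.118 (upper limit 0.239), 19/1314 gives 0.014 (0.022) and 34/1314 gives 0.026 (0.036), all as printed in SAP section 8.

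**Effect per omitted subject.** 1/120 = 0.83 points; 1/130 = 0.77 points. For zero events the upper limit is 1 − 0.025^(1/N): 3.03% at N = 120 and 2.80% at N = 130.

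| Device-related SAE subjects, first-device events counted | Proportion (exact 95% CI) | If all drop out under the reset |
|---|---|---|
| 1 of 120 | 0.83% (0.02 to 4.56) | 0/120 = 0% (0 to 3.03) |
| 1 of 130 | 0.77% (0.02 to 4.21) | 0/130 = 0% (0 to 2.80) |
| 2 of 130 | 1.54% (0.19 to 5.45) | 0/130 = 0% (0 to 2.80) |
| 4 of 130 | 3.08% (0.84 to 7.69) | 0/130 = 0% (0 to 2.80) |

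The number omitted, k, is an assumption ranging from 0 to 4; four is the number of revised subjects, not an observed count of SAEs.

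**Direction.** Let a = subjects whose only device-related SAEs came before replacement, and b = subjects whose only such SAEs came on the second device, more than 6 months after first implant.
- Against a window from first implant to the restarted 6-month visit: reset − extended = −a/N, so the reset can only lower the proportion.
- Against a fixed 6 months from first implant: reset − fixed = (b − a)/N. At N = 120, a = 1 and b = 0 gives −0.83 points; a = 0 and b = 1 gives +0.83 points. The sign is open because the reset also lengthens follow-up on the second device.

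**Observation time if counting starts at first implant and ends at the restarted visit.** With Table 8 windows kept, the longest spans are 194 + 194 = 388 days (6-month endpoint) and 194 + 374 = 568 days (12-month endpoint). These are not firm limits. Protocol 7.5.9.16 keeps a window open until the next visit occurs, and SAP 5.1.3 analyses by nominal visit. With the next visit at its latest Table 8 day (284 for Month 9, 561 for Month 18), the spans become 284 + 284 = 568 and 284 + 561 = 845 days, and late visits could exceed them.

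**The case against.** The endpoint wording sets no lower limit. SAP 5.1.2 assigns study days but contains no exclusion rule, and it sits under general principles that give way to more specific text. It also uses the qualifier *as appropriate*. SAP 5.7 deals mainly with repeated visits and efficacy data. SAP 5.6.1.1 presumes event-free status only for subjects who exit without an event. All of this makes the cumulative reading possible, but none of it states that first-device events count. The qualifier most naturally selects among implant, attempt and replacement dates by type of subject.

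The signal is also kept elsewhere. SAP 5.9 summarises all Phase II AEs over the study, and "All AEs and SAEs will also be summarized by relatedness". The stopping rules count fractures, dislodgements and revisions cumulatively. This limits the harm, but those outputs do not define the numerator of the primary safety endpoint.

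On size, no SADEs are reported, so on the documents' own figures the four revised subjects contributed none. Phase I agrees: seven revisions and eight SAEs, none of them device-related. The upper end of the 0-to-4 range is therefore hypothetical. Finally, a fixed 6 months from first implant is also a defensible window. That bears on the choice of remedy, not on whether a rule is needed.

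**Conclusion.** The concern holds. The reset of safety day 0 is an explicit rule, and on a natural reading it removes first-device device-related SAEs from both safety proportions for subjects replaced before the Month 6 assessment. Later replacements keep the original schedule and are unaffected. The shift is 0.83 points per omitted subject at N = 120, and the realised effect may be nil. Only the estimate and its interval are affected: there is no type I error consequence, and the events are not lost from all safety reporting. It should be corrected before the analysis. Confidence is medium, because the cumulative reading is open and the number of replacements before Month 6 is not given.

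**What to change.** In SAP 5.1.2 and 5.6.1.1, set safety day 0 at the first implant or implant attempt for every subject. Count each subject once for any device-related SAE from that date through the 6-month (or 12-month) visit of the current schedule, whichever device was in place. In SAP 5.7, Protocol 6.3 and Protocol 7.5.8.9, state that the replacement-date reset governs visit scheduling and efficacy data, and hence the end of the safety window, but not the start of safety counting. Report the number of replaced subjects, and flag counted events that fall more than 6 (or 12) months after first implant. A reader can then recover the fixed-window proportion.

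The cost is one sentence in each of the two SAP sections and one clarification in each of the other three places, with no new data. The downside is the longer observation of replaced subjects shown above, which is the reason for the flag. SAP section 6 provides for amendment before analysis; if the analysis has already been run, the study report should say which rule was used.
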